14 ADMINISTRATIVE AND ETHICAL CONSIDERATIONS

14.1 Regulatory and Ethical Compliance

This protocol was designed and will be conducted and reported in accordance with the International Conference on Harmonization (ICH) Harmonized Tripartite Guidelines for Good Clinical Practice, the Declaration of Helsinki, and applicable federal, state, and local regulations.

14.2 DUHS Institutional Review Board and DCI Cancer Protocol Committee

The protocol, informed consent form, advertising material, and additional protocol-related documents must be submitted to the DUHS Institutional Review Board (IRB) and DCI Cancer Protocol Committee (CPC) for review. The study may be initiated only after the Principal Investigator has received written and dated approval from the CPC and IRB.

The Principal Investigator must submit and obtain approval from the IRB for all subsequent protocol amendments and changes to the informed consent form. The CPC should be informed about any protocol amendments that potentially affect research design or data analysis (i.e. amendments affecting subject population, inclusion/exclusion criteria, agent administration, statistical analysis, etc.).

The Principal Investigator must obtain protocol re-approval from the IRB within 1 year of the most recent IRB approval. The Principal Investigator must also obtain protocol re-approval from the CPC within 1 year of the most recent IRB approval, for as long as the protocol remains open to subject enrollment.

14.3 Informed Consent

The informed consent form must be written in a manner that is understandable to the subject population. Prior to its use, the informed consent form must be approved by the IRB.

The Principal Investigator or authorized key personnel will discuss with the potential subject the purpose of the research, methods, potential risks and benefits, subject concerns, and other study-related matters. This discussion will occur in a location that ensures subject privacy and in a manner that minimizes the possibility of coercion. Appropriate accommodations will be made available for potential subjects who cannot read or understand English or are visually impaired. Potential subjects will have the opportunity to contact the Principal investigator or authorized key personnel with questions, and will be given as much time as needed to make an informed decision about participation in the study.

Before conducting any study-specific procedures, the Principal Investigator must obtain written informed consent from the subject or a legally acceptable representative. The original informed consent form will be stored with the subject's study records, and a copy of the informed consent form will be provided to the subject. The Principal Investigator is responsible for asking the subject whether the subject wishes to notify his/her primary care physician about participation in the study. If the subject agrees to such notification, the Principal Investigator will inform the subject's primary care physician about the subject's participation in the clinical study.

14.4 Study Documentation

Study documentation includes but is not limited to source documents, case report forms (CRFs), monitoring logs, appointment schedules, study team correspondence with sponsors or regulatory bodies/committees, and regulatory documents that can be found in the DCI-mandated "Regulatory Binder", which includes but is not limited to signed protocol and amendments, approved and signed informed consent forms, FDA Form 1572, CAP and CLIA laboratory certifications, and clinical supplies receipts and distribution records.

Source documents are original records that contain source data, which is all information in original records of clinical findings, observations, or other activities in a clinical trial necessary for the reconstruction and evaluation of the trial. Source documents include but are not limited to hospital records, clinical and office charts, laboratory notes, memoranda, subjects' diaries or evaluation checklists, pharmacy dispensing records, recorded data from automated instruments, copies or transcriptions certified after verification as being accurate copies, microfiches, photographic negatives, microfilm or magnetic media, x-rays, subject files, and records kept at the pharmacy, at the laboratories and at medico-technical departments involved in the clinical trial. When possible, the original record should be retained as the source document. However, a photocopy is acceptable provided that it is a clear, legible, and an exact duplication of the original document.

A REDCap case report form (CRF) will be the primary data collection document for the study. The CRFs will be updated within two weeks of acquisition of new source data. Only investigators and research nurse staff are permitted to make entries, changes, or corrections in the CRF. For paper CRFs, errors will be crossed out with a single line, and this line will not obscure the original entry. Changes or corrections will be dated, initialed, and explained (if necessary). The investigators or authorized key personnel will maintain a record of the changes and corrections. For electronic CRFs, an audit trail will be maintained by the REDCap CRF management system.

14.5 Privacy, Confidentiality, and Data Storage

The Principal Investigator will ensure that subject privacy and confidentiality of the subject's data will be maintained. Research Data Security Plans (RDSPs) will be approved by the appropriate institutional Site Based Research group.

To protect privacy, every reasonable effort will be made to prevent undue access to subjects during the course of the study. Prospective participants will be consented in an exam room where it is just the research staff, the patient and his family, if desired. For all future visits, interactions with research staff (study doctors and study coordinators) regarding research activities will take place in a private exam room. All research related interactions with the participant will be conducted by qualified research staff who are directly involved in the conduct of the research study.

To protect confidentiality, subject files in paper format will be stored in secure cabinets under lock and key accessible only by the research staff. Subjects will be identified only by a unique study number and subject initials. Electronic records of subject data will be maintained using a dedicated database (REDCap), which is housed in an encrypted and password-protected drive. Access to electronic databases will be limited to the research study team in the Department of Radiation oncology.

Upon completion of the study, research records will be archived and handled per DUHS HRPP policy.

Subject names or identifiers will not be used in reports, presentations at scientific meetings, or publications in scientific journals.

14.6 Data and Safety Monitoring

Data and Safety Monitoring will be performed in accordance with the DCI Data and Safety Monitoring Plan. For a more detailed description of the DSMP for this protocol, refer to Section 11 (Sections 11.3 and 11.4 in particular) along with section 12.

14.7 Protocol Amendments

All protocol amendments must be initiated by the Principal Investigator and approved by the IRB prior to implementation. IRB approval is not required for protocol changes that occur to protect the safety of a subject from an immediate hazard. However, the Principal Investigator must inform the IRB and all other applicable regulatory agencies of such action immediately.

14.8 Records Retention

The Principal Investigator will maintain study-related records for the longer of a period of:

- at least six years after study completion


16 Appendix A: GPA Criteria for NSCLC, Melanoma, Breast, Renal Cell & GI Cancers

GPA score: Graded prognostic assessment (GPA), is a prognostic index for patients with brain metastases based on histology. Sperduto et al [16], reported that the diagnosis-specific GPA is the least subjective, most quantitative and easiest tool to use based on a multi-institutional database of 3,900 patients with brain metastases.

Non-small-cell and small-cell lung cancer		GPA Scoring Criteria			Patient Score		
Prognostic Factor		0	0.5	1.0			
Age, years	> 60	50-60	< 50		—		
KPS	< 70	70-80	90-100		—		
ECM	Present	—	Absent		—		
No. of BM	> 3	2-3	1		—		
Sum total					—		
Median survival (months) by GPA: 0-1.0 = 3.0; 1.5-2.0 = 5.5; 2.5-3.0 = 9.4; 3.5-4.0 = 14.8							
Melanoma		GPA Scoring Criteria			Patient Score		
Prognostic Factor		0	1.0	2.0			
KPS	< 70	70-80	90-100		—		
No. of BM	> 3	2-3	1		—		
Sum total					—		
Median survival (months) by GPA: 0-1.0 = 3.4; 1.5-2.0 = 4.7; 2.5-3.0 = 8.8; 3.5-4.0 = 13.2							
Breast cancer		GPA Scoring Criteria				Patient Score	
Prognostic Factor		0	0.5	1.0	1.5	2.0	
KPS	≤ 50	60	70-80	90-100	n/a		—
Subtype	Basal	n/a	LumA	HER2	LumB		—
Age, years	≥ 60	< 60	n/a	n/a	n/a		—
Sum total							—
Median survival (months) by GPA: 0-1.0 = 3.4; 1.5-2.0 = 7.7; 2.5-3.0 = 15.1; 3.5-4.0 = 25.3							
Renal cell carcinoma		GPA Scoring Criteria			Patient Score		
Prognostic Factor		0	1.0	2.0			
KPS	< 70	70-80	90-100		—		
No. of BM	> 3	2-3	1		—		
Sum total					—		
Median survival (months) by GPA: 0-1.0 = 3.3; 1.5-2.0 = 7.3; 2.5-3.0 = 11.3; 3.5-4.0 = 14.8							
GI cancers		GPA Scoring Criteria				Patient Score	
Prognostic Factor		0	1	2	3	4	
KPS	< 70	70	80	90	100		—
Median survival (months) by GPA: 0-1.0 = 3.1; 2.0 = 4.4; 3.0 = 6.9; 4.0 = 13.5							

Abbreviations: Breast Subtype: Basal= Triple Negative (ER/PR/HER2-), LumA: (ER/PR positive, HER2 negative); LumB = (triple positive); HER2= (ER/PR negative, HER2 positive); brain metastases (BM), extracranial metastases (ECM); ER = estrogen receptor; HER = human epidermal growth factor receptor 2; KPS = Karnofsky performance score; LumA = luminal A; LumB =luminal B; PR = progesterone receptor. [16].

[figure not shown]
17 Appendix B: GPA Criteria for Other Cancer Histology

For histologies that are not listed above and are not excluded, GPA will be calculated using the following generalized formula from Sperduto et al [Sperduto PW1, Berkey B, Gaspar LE, Mehta M, Curran W.A new prognostic index and comparison to three other indices for patients with brain metastases: an analysis of 1,960 patients in the RTOG database. *Int J Radiat Oncol Biol Phys.* 2008 Feb 1;70(2):510-4.]

	Score		
	0	0.5	1.0
Age	>60	50–59	<50
KPS	<70	70–80	90–100
No. of CNS metastases	>3	2–3	1
Extracranial metastases	Present	—	None

Abbreviations: KPS = Karnofsky Performance Status; CNS = central nervous system.

GRADED PROGNOSTIC ASSESSMENT

18 Appendix C: Stereotactic Radiotherapy QA Guidelines

Below is the direct link to the RTOG Stereotactic Radiotherapy Quality Assurance Guidelines:

<http://dx.doi.org/10.1016/j.prro.2011.06.014>

19 Appendix D: Performance Status

KARNOFSKY PERFORMANCE SCALE

100	Normal; no complaints; no evidence of disease
90	Able to carry on normal activity; minor signs or symptoms of disease
80	Normal activity with effort; some sign or symptoms of disease
70	Cares for self; unable to carry on normal activity or do active work
60	Requires occasional assistance, but is able to care for most personal needs
50	Requires considerable assistance and frequent medical care
40	Disabled; requires special care and assistance
30	Severely disabled; hospitalization is indicated, although death not imminent
20	Very sick; hospitalization necessary; active support treatment is necessary
10	Moribund; fatal processes progressing rapidly
0	Dead

ZUBROD PERFORMANCE SCALE

0	Fully active, able to carry on all predisease activities without restriction (Karnofsky 90-100).
1	Restricted in physically strenuous activity but ambulatory and able to carry out work of a light or sedentary nature. For example, light housework, office work (Karnofsky 70-80).
2	Ambulatory and capable of all self-care but unable to carry out any work activities. Up and about more than 50% of waking hours (Karnofsky 50-60).
3	Capable of only limited self-care, confined to bed or chair 50% or more of waking hours (Karnofsky 30-40).
4	Completely disabled. Cannot carry on any self-care. Totally confined to bed or chair (Karnofsky 10-20).
5	Dead

20 Appendix E: The Mini-Mental State Exam Instructions and Exam

**Instructions for Administration of
Mini-Mental State Examination (MMSE)**

Orientation	
 1. Ask for the Date. Then ask specifically for parts omitted, eg, "Can you also tell me what season it is?" Score one point for each correct answer. 2. Ask in turn, "Can you tell me the name of this hospital?" (town, county, etc.) Score one point for each correct answer.
Registration	
Ask the patient if you may test his/her memory. Then say the names of 3 unrelated objects, clearly and slowly, about one second for each. After you have said all 3, ask the patient to repeat them. This first repetition determines his/her score (0-3) but keep saying them until he/she can repeat all 3, up to 6 trials. If all 3 are not eventually learned, recall cannot be meaningfully tested.

Attention and Calculation	
Ask the patient to spell the word "world" backwards. The score is the numbers of letters in correct order (e.g, DLROW=5; DLRW=4; DLORW, DLW=3; OW=2; DRLWO=1).

Recall	
Ask the patient if he/she can recall the 3 words you previously asked him/her to remember. Score 0 – 3.

Language	
Naming: Show the patient a wristwatch and ask him/her what it is. Repeat for pencil. Score 0 – 2.

	
Repetition: Ask the patient to repeat the sentence after you.
 
Allow only one trial. Score 0 – 1.

	
3-stage command: Give the patient a piece of plain blank paper and repeat the command. Score 1 point for each part correctly executed.

	
Reading: On a blank piece of paper print the sentence, “Close your eyes,” in letters large enough for the patient to see clearly. Ask him/her to read it and do what it says. Score 1 point only if he actually closes his eyes.

	
Writing: Give the patient a blank piece of paper and ask him/her to write a sentence for you. Do not Dictate a sentence; it is to be written spontaneously. It must contain a subject and verb and be sensible. Correct grammar and punctuation are not necessary.

	
Copying: On a clean piece of paper, draw intersecting pentagons, each side about 1 in., and ask him/her to copy it exactly as it is. All 10 angles must be present and 2 must intersect to score 1 point. Tremor and rotation are ignored.

MINI MENTAL STATUS EXAMINATION

Patient _____ Examiner _____ Date _____

Maximum Score

Orientation

- 5 () What is the (year) (season) (date) (day) (month)?
- 5 () Where are we (state) (country) (town) (hospital) (floor)?

Registration

- 3 () Name 3 Common objects (eg, "apple," "table," "penny"). Take 1 second to say each. Then ask the patient to repeat all 3 after you have said them. Give 1 point for each correct answer. Then repeat them until he/she learns all 3. Count trials and record. Trials _____

Attention and Calculation

[figure not shown]
- 5 () Serial 7's. 1 point for each correct answer. Stop after 5 answers. Alternatively, spell "world" backwards. The score is the number of letters in correct order (D__L__R__O__W__).

Recall

- 3 () Ask for the 3 objects repeated above. Give 1 point for each correct answer. [Note: recall cannot be tested if all 3 objects were not remembered during registration]

Language

- 2 () Name a pencil and watch.
- 1 () Repeat the following "No ifs, ands, or buts"
- 3 () Follow a 3-stage command:
"Take a paper in your hand, fold it in half, and put it on the floor."
- 1 () Read and obey the following: CLOSE YOUR EYES
- 1 () Write a sentence.
- 1 () Copy the design shown.

Total Score

ASSESS level of consciousness along a continuum _____

Alert Drowsy Stupor Coma

"MINI-MENTAL STATE." A PRACTICAL METHOD FOR GRADING THE COGNITIVE STATE OF PATIENTS FOR THE CLINICIAN. *Journal of Psychiatric Research*, 12(3): 189-198, 1975.

21 Appendix F TRAIL MAKING TEST

PART A

Sample Instructions: “On this page (point) are some numbers. Begin at number 1 (point to ‘1’) and draw a line from 1 to 2 (point to ‘2’), 2 to 3 (point to ‘3’), 3 to 4 (point to ‘4’), and so on, in order, until you reach the end (point to circle marked END). Draw the lines as fast as you can. Ready, begin. (If the patient makes a mistake, point out the error and explain it. If the patient completes Sample A correctly, say “Good! Let’s try the next one.” Proceed with the test and repeat instructions above. Start timing as soon as the instruction is given to “begin.” Watch closely in order to catch any errors as soon as they are made. If the patient makes an error during the test, call it to his/her attention immediately and have him/her proceed from the point the mistake occurred. DO NOT STOP TIMING. The patient must complete the test in 3 minutes or less.)”

Test Instructions: “On this page are numbers from 1 to 25. Do this the same way. Begin at number one (point to ‘1’) and draw a line from one to two (point to ‘2’), two to three (point to ‘3’), three to four (point to ‘4’), and so on, in order until you reach the end (point to circle marked ‘End’). Remember, work as fast as you can. Ready! Begin!”

I. Trail Making Test Part A:

1. Did the patient do Sample A before attempting Part A? Yes No

2. Total amount of time the patient was tested: __ : __ (min:sec)

3. Did the patient reach the “END” of the test?

Yes

No, tested for 3 minutes OR No, tested for <3 minutes

If No, specify the last number reached on the test: __ __

Comments: _____

PART B

Sample Instructions: “On this page (point) are some numbers and letters. Begin at number 1 (point to ‘1’) and draw a line from 1 to A (point to ‘A’), A to 2 (point to ‘2’), 2 to B (point to ‘B’), B to 3 (point to ‘3’), 3 to C (point to ‘C’) and so on, in order, until you reach the end (point to circle marked ‘End’). Remember, you first have a number (point to ‘1’), then a letter (point to ‘A’), then a number (point to ‘2’), then a letter (point to ‘B’), and so on. Draw the lines as fast as you can. Ready, begin. (If the patient makes a mistake, point out the error and explain it. If the patient completes Sample B correctly, say “Good! Let’s try the next one.” Proceed with the test and repeat instructions above. Start timing as soon as the instruction is given to “begin.” Watch closely in order to catch any errors as soon as they are made. If the patient makes an error during the test, call it to his/her attention immediately and have

him/her proceed from the point the mistake occurred. DO NOT STOP TIMING. The patient must complete the test in 5 minutes or less.)”

Test Instructions: “On this page are both numbers and letters. Do this the same way. Begin at number one (point to ‘1’) and draw a line from one to A (point to ‘A’), A to two (point to ‘2’), two to B (point to ‘B’), B to three (point to ‘3’), three to C (point to ‘C’), and so on, in order, until the end (point to circle marked ‘END’). Remember, first you have a number (point to ‘1’), then a letter (point to ‘A’), and so on. Do not skip around, but go from one circle to the next in the proper order. Draw the lines as fast as you can. Ready! Begin!”

II. Trail Making Test Part B:

1. Did the patient do Sample B before attempting Part B? Yes No

2. Total amount of time the patient was tested: _ : _ _ (min:sec)

3. Did the patient reach the “END” of the test?

Yes

No, tested for 5 minutes OR No, tested for <5 minutes

If No, specify the last number/letter reached on the test: _ _

[figure not shown]
[figure not shown]
Comments: _____

Trail Making (continued)

TRAIL MAKING

Part A

[figure not shown]
[figure not shown]
Sample

TRAIL MAKING

Part B

Sample

22 Appendix G: FACT-Br

FACT-Br (Version 4)

Below is a list of statements that other people with your illness have said are important. By **circling one (1) number per line**, please indicate how true each statement has been for you **during the past 7 days.**

PHYSICAL WELL-BEING		Not at all	A little bit	Some-what	Quite a bit	Very much
GP1	I have a lack of energy.....	0	1	2	3	4
GP2	I have nausea.....	0	1	2	3	4
GP3	Because of my physical condition, I have trouble meeting the needs of my family.....	0	1	2	3	4
GP4	I have pain.....	0	1	2	3	4
GP5	I am bothered by side effects of treatment.....	0	1	2	3	4
GP6	I feel ill.....	0	1	2	3	4
GP7	I am forced to spend time in bed	0	1	2	3	4

SOCIAL/FAMILY WELL-BEING		Not at all	A little bit	Some-what	Quite a bit	Very much
GS1	I feel close to my friends	0	1	2	3	4
GS2	I get emotional support from my family.....	0	1	2	3	4
GS3	I get support from my friends.....	0	1	2	3	4
GS4	My family has accepted my illness.....	0	1	2	3	4
GS5	I am satisfied with family communication about my illness	0	1	2	3	4
GS6	I feel close to my partner (or the person who is my main support).....	0	1	2	3	4
Q1	Regardless of your current level of sexual activity, please answer the following question. If you prefer not to answer it, please check this box  and go to the next section.					
GS7	I am satisfied with my sex life.....	0	1	2	3	4

FACT-Br (Version 4)

By circling one (1) number per line, please indicate how true each statement has been for you during the past 7 days.

EMOTIONAL WELL-BEING

		Not at all	A little bit	Some- what	Quite a bit	Very much
GE1	I feel sad.....	0	1	2	3	4
GE2	I am satisfied with how I am coping with my illness	0	1	2	3	4
GE3	I am losing hope in the fight against my illness	0	1	2	3	4
GE4	I feel nervous	0	1	2	3	4
GE5	I worry about dying	0	1	2	3	4
GE6	I worry that my condition will get worse.....	0	1	2	3	4

FUNCTIONAL WELL-BEING

		Not at all	A little bit	Some- what	Quite a bit	Very much
GF1	I am able to work (include work at home).....	0	1	2	3	4
GF2	My work (include work at home) is fulfilling	0	1	2	3	4
GF3	I am able to enjoy life	0	1	2	3	4
GF4	I have accepted my illness	0	1	2	3	4
GF5	I am sleeping well.....	0	1	2	3	4
GF6	I am enjoying the things I usually do for fun.....	0	1	2	3	4
GF7	I am content with the quality of my life right now	0	1	2	3	4

FACT-Br (Version 4)

By circling one (1) number per line, please indicate how true each statement has been for you during the past 7 days.

ADDITIONAL CONCERNS		Not at all	A little bit	Some- what	Quite a bit	Very much
Br1	I am able to concentrate	0	1	2	3	4
Br2	I have had seizures (convulsions)	0	1	2	3	4
Br3	I can remember new things	0	1	2	3	4
Br4	I get frustrated that I cannot do things I used to	0	1	2	3	4
Br5	I am afraid of having a seizure (convulsion)	0	1	2	3	4
Br6	I have trouble with my eyesight.....	0	1	2	3	4
Br7	I feel independent	0	1	2	3	4
NTX 6	I have trouble hearing	0	1	2	3	4
Br8	I am able to find the right word(s) to say what I mean.....	0	1	2	3	4
Br9	I have difficulty expressing my thoughts.....	0	1	2	3	4
Br10	I am bothered by the change in my personality	0	1	2	3	4
Br11	I am able to make decisions and take responsibility.....	0	1	2	3	4
Br12	I am bothered by the drop in my contribution to the family	0	1	2	3	4
Br13	I am able to put my thoughts together	0	1	2	3	4
Br14	I need help in caring for myself (bathing, dressing, eating, etc.).....	0	1	2	3	4
Br15	I am able to put my thoughts into action	0	1	2	3	4
Br16	I am able to read like I used to.....	0	1	2	3	4
Br17	I am able to write like I used to	0	1	2	3	4
Br18	I am able to drive a vehicle (my car, truck, etc.)	0	1	2	3	4
Br19	I have trouble feeling sensations in my arms, hands, or legs	0	1	2	3	4
Br20	I have weakness in my arms or legs	0	1	2	3	4
Br21	I have trouble with coordination.....	0	1	2	3	4
As 10	I get headaches.....	0	1	2	3	4

23 Appendix H: Hopkins Verbal Learning Test

HOPKINS VERBAL LEARNING TEST
 Form 1: four-legged animals, precious stones, human dwellings

Part A: Free Recall

	Trial 1	Trial 2	Trial 3		
EMERALD	_____	_____	_____		
HORSE	_____	_____	_____		
TENT	_____	_____	_____		
SAPPHIRE	_____	_____	_____		
HOTEL	_____	_____	_____		
CAVE	_____	_____	_____		
OPAL	_____	_____	_____		
TIGER	_____	_____	_____		
PEARL	_____	_____	_____		
COW	_____	_____	_____		
HUT	_____	_____	_____		
# CORRECT	_____	_____	_____		
HORSE	ruby*	CAVE	balloon	coffee	LION
house*	OPAL	TIGER	boat	scarf	PEARL
HUT	EMERALD	SAPPHIRE	dog*	apartment*	penny
TENT	mountain	cat*	HOTEL	COW	diamond*

Part B: Recognition:

True-Positives: _____/12

False-Positive Errors: Related: _____/6 Unrelated: _____/6

Discrimination Index: (# True-Positives) – (# False-Positives) = _____

HOPKINS VERBAL LEARNING TEST
Form 2: kitchen utensils, alcoholic beverages, weapons

Part A: Free Recall

	Trial 1	Trial 2	Trial 3
FORK	_____	_____	_____
RUM	_____	_____	_____
PAN	_____	_____	_____
PISTOL	_____	_____	_____
SWORD	_____	_____	_____
SPATULA	_____	_____	_____
BOURBON	_____	_____	_____
VODKA	_____	_____	_____
POT	_____	_____	_____
COW	_____	_____	_____
HUT	_____	_____	_____
WINE	_____	_____	_____
# CORRECT	_____	_____	_____

Part B: Recognition:

spoon*	PISTOL	doll	whiskey*	FORK	POT
harmonica	can opener*	SWORD	pencil	gun*	VODKA
knife*	RUM	trout	BOMB	PAN	gold
WINE	lemon	SPATULA	BOURBON	beer*	RIFLE

True-Positives: _____ /12

False-Positive Errors: Related: _____ /6 Unrelated: _____ /6

Discrimination Index: (# True-Positives) – (# False-Positives) = _____

HOPKINS VERBAL LEARNING TEST
Form 3: musical instruments, fuels, food flavorings

Part A: Free Recall

	Trial 1	Trial 2	Trial 3
SUGAR	_____	_____	_____
TRUMPET	_____	_____	_____
VIOLIN	_____	_____	_____
COAL	_____	_____	_____
GARLIC	_____	_____	_____
KEROSINE	_____	_____	_____
VANILLA	_____	_____	_____
WOOD	_____	_____	_____
CLARINET	_____	_____	_____
FLUTE	_____	_____	_____
CINNAMON	_____	_____	_____
GASOLINE	_____	_____	_____
# CORRECT	_____	_____	_____

Part B: Recognition:

pepper*	GARLIC	WOOD	drum*	oil*	SUGAR
Harmonica	salt*	priest	chair	COAL	CLARINET
TRUMPET	basement	CINNAMON	FLUTE	electricity*	Moon
KEROSINE	VANILLA	GASOLINE	sand	piano*	VIOLIN

True-Positives: _____ /12

False-Positive Errors: Related: _____ /6 Unrelated: _____ /6

Discrimination Index: (# True-Positives) – (# False-Positives) = _____

HOPKINS VERBAL LEARNING TEST
Form 4: birds, articles of clothing, carpenter's tools

Part A: Free Recall

	Trial 1	Trial 2	Trial 3
CANARY	_____	_____	_____
SHOES	_____	_____	_____
EAGLE	_____	_____	_____
BLOUSE	_____	_____	_____
NAILS	_____	_____	_____
CROW	_____	_____	_____
BLUEBIRD	_____	_____	_____
SCREWDRIVER	_____	_____	_____
PANTS	_____	_____	_____
CHISEL	_____	_____	_____
SKIRT	_____	_____	_____
WRENCH	_____	_____	_____
# CORRECT	_____	_____	_____

Part B: Recognition:

BLUEBIRD	shirt*	CHISEL	EAGLE	chocolate	robin*
chapel	SCREWDRIVER	CROW	sparrow*	WRENCH	PANTS
NAILS	socks*	child	SHOES	hair	hammer*
CANARY	apple	SKIRT	saw*	silver	BLOUSE

True-Positives: _____/12

False-Positive Errors: Related: _____/6 Unrelated: _____/6

Discrimination Index: (# True-Positives) – (# False-Positives) = _____

HOPKINS VERBAL LEARNING TEST
Form 5: occupations/professions, sports, vegetables

Part A: Free Recall

	Trial 1	Trial 2	Trial 3
TEACHER	_____	_____	_____
BASKETBALL	_____	_____	_____
LETTUCE	_____	_____	_____
DENTIST	_____	_____	_____
TENNIS	_____	_____	_____
BEAN	_____	_____	_____
ENGINEER	_____	_____	_____
POTATO	_____	_____	_____
PROFESSOR	_____	_____	_____
GOLF	_____	_____	_____
CORN	_____	_____	_____
SOCCER	_____	_____	_____
# CORRECT	_____	_____	_____

Part B: Recognition:

True-Positives: _____/12

TENNIS	football*	PROFESSOR	spinach*	lawyer*	submarine
GOLF	DENTIST	LETTUCE	spider	water	BEAN
BASKETBALL	doctor*	CORN	baseball*	TEACHER	snake
carrot*	ENGINEER	glove	SOCCER	POTATO	tulip

False-Positive Errors: Related: _____/6 Unrelated: _____/6

Discrimination Index: (# True-Positives) – (# False-Positives) = _____

HOPKINS VERBAL LEARNING TEST
Form 6: fish, parts of a building, phenomens

Part A: Free Recall

	Trial 1	Trial 2	Trial 3
SHARK	_____	_____	_____
WALL	_____	_____	_____
HERRING	_____	_____	_____
RAIN	_____	_____	_____
FLOOR	_____	_____	_____
HAIL	_____	_____	_____
CATFISH	_____	_____	_____
ROOF	_____	_____	_____
SALMON	_____	_____	_____
STORM	_____	_____	_____
CEILING	_____	_____	_____
SNOW	_____	_____	_____
# CORRECT	_____	_____	_____

Part B: Recognition:

True-Positives: _____ /12

HAIL	bass*	SNOW	bank	FLOOR	mustard
window*	CEILING	canyon	RAIN	ladder	STORM
HERRING	SALMON	tornado*	trout*	melon	ROOF
SHARK	hurricane*	elbow	CATFISH	WALL	door*

False-Positive Errors: Related: _____ /6 Unrelated: _____ /6

Discrimination Index: (# True-Positives) – (# False-Positives) = _____

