5 OBJECTIVES AND ENDPOINTS

	Objective	Endpoint	Analysis
Primary	Assess the impact of using SIMT SRS for the treatment of brain metastases on survival	Proportion of patients who live longer than predicted according to the Graded Prognostic Assessment (GPA) score	See Section 13.4
Key Secondary	Describe the time to local brain recurrence	Proportion of patients that experience local brain recurrence within 1 year of SIMT SRS treatment.	See Section 13.5.1
Other Secondary	Describe the time to distant brain recurrence	Proportion of patients that experience a new brain metastasis at a site different from the original brain metastasis site 1 year after SIMT SRS treatment	See Section 13.5.2
Other Secondary	Describe the time to death due to neurological causes	Proportion of patients who are dead within 1 year of SIMT SRS treatment due to neurologic reasons	See Section 13.5.2
Other Secondary	Describe the prevalence of significant adverse events	Proportion of patients who experience grade 3, 4, or 5 neurologic adverse events attributable to SIMT SRS	See Section 13.5.2
Key Exploratory	Describe changes over time in neurocognition	Mean changes from baseline in subscales of the Trailmaking instruments and the HLVT	See Section 13.6.1
Key Exploratory	Describe changes over time in quality of life	Mean changes from baseline in subscales of the FACT-Brain instrument	See Section 13.6.1
Other Exploratory	Quantify treatment set up and dosimetric data for this treatment technique	Mean length of time to set-up and treat patient, Volume of brain exposed to 12Gy, Mean PTV dose, Total volume of all brain metastases, conformity index, maximum dose	See Section 13.6.2
Other Exploratory	Describe the rate of salvage therapy	The proportion of patients who receive salvage treatment after failing SIMT SRS	See Section 13.6.2
Other Exploratory	Describe prevalence of radionecrosis at the SRS site	Proportion of patients with radionecrosis at the SRS site; the proportion of lesions showing radionecrosis	See Section 13.6.2
Other Exploratory	Describe length and intensity of steroid usage post-SRS	Descriptive statistics	See Section 13.6.2

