13.6.1 Key Exploratory Objectives

The mean changes from baseline in neurocognition as measured by Trailmaking A and B, the MMSE and the HVLT will be summarized. Similarly, the mean changes from baseline in quality of life as measured by the FACT-Brain, will be summarized.

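### Appendix H: the recall list of HVLT Form 2 does not match its own recognition targets, which can put up to a 2-point artefact into recognition change scores if the sheet is used as printed and forms differ between visits

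*Combined protocol and SAP*

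**What the plan says.** Appendix H prints six HVLT forms. Each has a free-recall list given over three trials and a 24-word recognition grid in which targets are in capitals, related distractors carry an asterisk and unrelated distractors are in lower case. True positives are scored out of 12, and the recognition score is "Discrimination Index: (# True-Positives) – (# False-Positives)".

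Form 2 is headed "Form 2: kitchen utensils, alcoholic beverages, weapons". Its recall list as printed is FORK, RUM, PAN, PISTOL, SWORD, SPATULA, BOURBON, VODKA, POT, COW, HUT, WINE. Two rows of its recognition grid read "knife* RUM trout BOMB PAN gold" and "WINE lemon SPATULA BOURBON beer* RIFLE", so BOMB and RIFLE count as targets.

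The HVLT feeds one key exploratory endpoint. The table in Section 5 gives it as "Mean changes from baseline in subscales of the Trailmaking instruments and the HLVT", and Section 13.6.1 says "The mean changes from baseline in neurocognition as measured by Trailmaking A and B, the MMSE and the HVLT will be summarized". No test is planned. Section 10.8.1 has the HVLT given at every visit. The documents do not say which form is used at which visit, whether forms rotate, or which HVLT score is analysed.

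**The concern.** A recognition trial is meant to test words the patient has heard. On Form 2 two of the 12 words counted as correct were never presented, so a patient who rightly says that BOMB and RIFLE were not on the list is marked as missing two targets. Two words the patient did learn, COW and HUT, are not in the grid at all. Form 2 therefore has a different recognition scale from Forms 3 to 6.

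The endpoint is change from baseline. If Form 2 is used at one visit and a sound form at another, part of the change comes from the sheet and not from the patient. The direction depends on the order: Form 2 at baseline produces apparent improvement, which could hide decline; Form 2 at follow-up produces apparent decline. The protocol's stated hypothesis (Section 3.1) includes the absence of a significant effect on neurocognition, so these scores will be read even though they are exploratory.

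**Working it through.** **Inputs.** The recall lists and capitalised recognition words of Appendix H; the scoring line on each form; the visit schedule in Section 10.5.

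**Step 1: structure of the grids.** Each of the six grids has 24 words: 12 targets, 6 related and 6 unrelated distractors. This reproduces the denominators of 12, 6 and 6 printed on the forms.

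**Step 2: match recall words to targets.**

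| Form | Recall words as read | Targets not in recall list | Recall words not in grid | Targets that were read out |
|---|---|---|---|---|
| 1 | 11 | LION | none | 11 (uncertain, see objection) |
| 2 | 12 | BOMB, RIFLE | COW, HUT | 10 |
| 3 to 6 (each) | 12 | none | none | 12 |

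**Step 3: categories on Form 2.** Utensils: FORK, PAN, SPATULA, POT (4). Drinks: RUM, BOURBON, VODKA, WINE (4). Weapons: PISTOL, SWORD (2). Left over: COW and HUT (2). Adding BOMB and RIFLE to the weapons and removing COW and HUT gives 4 + 4 + 4 = 12, which is exactly the form's own target set.

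**Step 4: effect on the recognition score.** Let h be the chance of recognising a word that was read out and g the chance of saying yes to a target that was not. Expected true positives are 10h + 2g on Form 2 and 12h on Forms 3 to 6. The gap is 12h − (10h + 2g) = 2(h − g).

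- Perfect memory, no guessing (h = 1, g = 0): 10 on Form 2, 12 on Forms 3 to 6, gap 2. With no false positives the discrimination index is also 10 against 12.
- Perfect memory, but yes to both unread weapons (h = 1, g = 1): 10 + 2 = 12, gap 0. So 10 is the perfect-memory, no-guessing score and not a hard maximum.

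**Step 5: effect on recall.** The three-trial ceiling is 3 × 12 = 36 on Form 2, the same as on Forms 3 to 6. The ceiling of total recall is intact.

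**Step 6: effect on change from baseline**, for a patient with perfect memory and no guessing.

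- Form 2, then one of Forms 3 to 6: 12 − 10 = +2 in recognition, 36 − 36 = 0 in total recall.
- One of Forms 3 to 6, then Form 2: 10 − 12 = −2 in recognition, 0 in total recall.
- The same form at both visits: 0.

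In such patients, with Form 2 and Forms 3 to 6 the only forms in use, the artefact in the mean change is 2 × (share given Form 2 at baseline − share given Form 2 at follow-up). It reaches +2 or −2 only if all patients have Form 2 at one of the two visits and none at the other. It is zero if the shares are equal.

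**Step 7: can forms differ between visits?** Section 10.5 with the pre-study test gives 1 baseline + 1 at about 4 weeks + 4 in year 1 + 2 in year 2 = up to 8 occasions for 6 forms. Changing forms is possible, but no section schedules it.

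**The case against.** **It may be a PDF-reading fault.** COW and HUT stand in the Form 1 table directly above Form 2, and tables in this text are known to be damaged. But a lost row removes a word; it does not insert two. COW and HUT are still present in Form 1's list, so they were not displaced from it. In Form 2 they sit inside a full 12-row list, before WINE, and exactly two targets are missing. Form 2 is wrong as written.

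**Form 1.** A reader might infer that Form 1 ("Form 1: four-legged animals, precious stones, human dwellings") is faulty too, because LION appears in the grid row "HORSE ruby* CAVE balloon coffee LION" but not in the 11-word recall list, giving 11 attainable targets and a recall ceiling of 3 × 11 = 33. The documents do not support calling this an error. The Form 1 table is visibly broken, with the recognition grid run into the recall table ahead of its Part B heading, and one lost row would explain everything. This is a point to check, not a finding.

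**The distortion is conditional.** A reader might infer that change from baseline is distorted. That requires staff to read from this sheet as printed and to use different forms at the two visits, and the documents establish neither. This objection stands, and the consequence is stated accordingly. It also stands that if total recall alone were analysed, Form 2 would have no ceiling effect.

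**It matters little.** The HVLT is one of several instruments in a descriptive endpoint. Patients may decline testing (Study Calendar, note 4), and testing stops after brain progression (Section 10.7.1). The decision rule in Section 13.8 does not use it, and the further factors named in Section 13.4.3 do not mention neurocognition. All true, and it limits the weight of the point. It does not make the mismatch merely clerical, because the sheet generates the scores that are analysed.

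**Conclusion.** The concern holds for Form 2. Its recall list contains two words from Form 1 and omits two of its own recognition targets, while Forms 3 to 6 match on all 12. The size is 10 against 12 true positives, and the same for the discrimination index, under perfect memory and no guessing; the gap is 2(h − g) more generally and shrinks as memory weakens or guessing on the unread targets rises. The possible artefact in recognition change is therefore up to 2 points in either direction. It rests on two assumptions that the documents do not settle: use of the sheet as printed, and different forms at baseline and follow-up. The primary endpoint, the sample size and the decision rule are unaffected. No conclusion is drawn about Form 1.

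**What to change.** 1. In Appendix H, replace COW and HUT in the Form 2 recall list with BOMB and RIFLE, so that the list equals the form's own 12 recognition targets. Form 2 then has 12 recall words, a recall ceiling of 36 and 12 matched targets, like Forms 3 to 6.
2. Look at the source page to see whether the Form 1 recall list really lacks LION or only lost a row on reading. Correct it only if the word is missing there.
3. Establish which form was given at each visit. If Form 2 was used as printed, flag those assessments.
4. As a sensitivity analysis, rescore Form 2 recognition on the 10 matched targets, leaving out BOMB and RIFLE, and express it as a proportion: a perfect patient then has 10/10 on Form 2 and 12/12 on Forms 3 to 6.

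Excluding Forms 1 and 2 from the analysis is not advised. If either served as the baseline form, every change score that depends on it would be lost, and Form 2 total recall, whose ceiling is intact, would be discarded as well.

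The cost is one corrected appendix page and a small rescoring analysis. The limitation is that rescoring is possible only where item-level recognition responses were kept; elsewhere the flagged scores can only be reported with the caveat.
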